represented by a prior distribution, with observed data, represented by the likelihood. This yields a posterior distribution from which statements about the probability of a given effect size can be made. As treatment outcomes accumulate over the course of the trial, posterior probabilities are used to estimate treatment effects and inform the pruning of less effective treatments based on a priori decision rules.

Designing an adaptive trial typically begins with a simulation study to address issues such as timing and frequency of interim analyses, and to understand the operating characteristics associated with the criteria for dropping conditions [57]. In keeping with the proposed DTL design, a Monte Carlo simulation study was conducted (see Statistical Analyses) to assess the relative merits of this design over a non-adaptive parallel-group approach. Simulation results, support the proposed DTL design in showing that under scenarios reflecting the hypothesized treatment effects, the adaptive design allocates more subjects to the more promising treatment conditions, i.e., appropriate “pruning” of less effective conditions. Using simulated data, the design performs well as demonstrated by adequate power and Type I error rates. Thus, employing the proposed DTL design is likely to yield the same conclusions as the classical fixed (non-adaptive) design, but with greater statistical precision for the most promising treatments.

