### **Study Design**

BD type I or II patients (n=160), on a depressive or mixed episode, who were on therapeutic doses of any of the commonly utilized mood stabilizing agents (lithium, anticonvulsants, atypical antipsychotics) for at least one month and who were still symptomatic (MADRAS >20) will be enrolled. Patients will be randomly assigned to orally receive one of 4 conditions: aspirin 1000 mg (2 capsules of 500 mg) qam, NAC 1000 mg (2 capsules of 500 mg) bid, combined aspirin and NAC at same doses as given individually or matched placebo, as an add-on medication to their ongoing treatment regimen, for an 16-week double-blind trial. After the first 8 week of the double blind treatment, the responders will keep taking the same study drug, whichever it is. And the non-responders will be re-randomized for one of the other three groups of study drugs they haven't tried yet.

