### **Statistical analyses:**

#### Simulation Study

In preparation of this application we conducted a Monte Carlo simulation study to assess the relative merits of the proposed DTL adaptive design over a non-adaptive, parallel-group approach. Specifically, the goal of this study was to demonstrate that the DTL design would result in the maximum number of subjects being treated in the most promising conditions, i.e., appropriate "pruning" of less effective conditions. Simulation scenarios including one that posits no effect across conditions and others, assuming specific anticipated effects, permits evaluation of Type I and Type II Error rates respectively. Sample size for each simulated trial was set at  $n = 160$ . Response to treatment was defined, dichotomously, as  $> 50\%$  decrease in depression score as measured on the MADRS. Specification of effects for the simulations assumed that the rate of response in the placebo condition is 25%, while 1000 mg aspirin qd and 1000 mg NAC bid have comparable effects with response rates of 50% each. The combination of 1000 mg aspirin qd and 1000 mg NAC bid is anticipated to demonstrate an additive effect yielding a 70% response rate. At 50% information gathering, defined as  $n = 80$  subjects having completed the study, a Bayesian interim analysis determined the posterior probability that treatment conferred benefit. Benefit was defined as the absolute difference in response rate for each treatment relative to placebo. The remaining 80 subjects were allocated to the retained (non-pruned) treatments, with the probability of assignment to any given group based on the number of groups continuing in the study.

Pruning/Retention Rules. Simulation scenarios considered a variety of pruning rules that varied in stringency for 1) detecting a clinically decisive difference ( $>10\%$  from placebo), and 2) selecting the best performing treatment. All simulations assumed a  $\sim\text{Beta}(1,1)$  prior distribution for the probability of treatment response in all study conditions. A  $\text{Beta}(1,1)$  prior models values within the range  $[0,1]$  in which all values have the same probability of occurring. This constitutes a vague, neutral prior distribution which reflects uncertainty preceding data accrual. At 50% of data gathering ( $n = 80$ ) the prior (i.e.  $\sim\text{Beta}(1,1)$ ) was updated with data generated from a binomial distribution for each

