condition. The posterior distributions of the differences between each treatment and placebo formed the basis of pruning decisions. A decisive difference is defined as occurring if the posterior probability of there being a <10% difference between any of the treatments and placebo was  $< 0.20$ . Another way of saying this is that if there was a >80% chance that the all treatment-placebo differences were <10% then the simulation concluded that the trial had failed to find a decisive difference. If this first rule identified the existence of a decisive difference for any of the treatments, the algorithm then selected the treatment that had the highest posterior probability of conferring benefit (i.e. the  $p(\text{treatment-control} > 0|\text{data})$  for participants. If the algorithm failed to identify a decisive treatment difference, the 1000 mg aspirin condition was retained as the active treatment. This was done to further our established programmatic goal of evaluating the anti-inflammatory effects of aspirin on depression by providing the most precise effect size estimate possible.

Study performance in terms of maximizing patients allocated to the best-performing conditions and for Type I and Type II Error rates are reported for the design under these retention/pruning criteria.

Simulation of Pruning/Retention Rules. Simulation evaluated the pruning rules for three scenarios. Scenario 1 simulated clinical trials with binomial probabilities of response of 0.25, 0.50, 0.50, and 0.70 for placebo, aspirin, NAC and aspirin + NAC respectively. Scenario 2 addressed the situation in which the effect sizes are less optimistic. Scenario 2 posited binomial probabilities of response of 0.25, 0.30, 0.30, and 0.50 for placebo, aspirin, NAC and aspirin + NAC respectively. Scenario 3 simulated clinical trials with binomial probabilities of response of 0.25, 0.25, 0.25 and 0.25 for placebo, aspirin, NAC and aspirin + NAC respectively. Since this last scenario simulates data in which there is no effect, the probability of identifying a decisive effect is an estimate of the Type I Error Rate for the pruning algorithm.

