If  $N = 160$  participants are randomized across four conditions in a 1:1:1:1 ratio, contrasts for treatment response rates versus placebo will use  $n = 40$  participants per cell. For Scenario 1, assuming  $n = 40$  per group and  $\alpha = 0.05$ , power to detect the difference between the proportions 0.25 and 0.50 is 65%. Using the same assumptions power to detect the difference between the proportions 0.25 and 0.70 is >99%. For Scenario 2, assuming  $n = 40$  per group and  $\alpha = 0.05$ , power to detect the difference between 0.25 and 0.5 is 65%. More generally, for comparison of two independent proportions, sample sizes of  $n = 40$  per group and  $\alpha = 0.05$  provide 80% power to detect a difference between 0.25 and 0.55. Such a sample is underpowered for two of the effects in Scenario 1, and all of the effects in Scenario 2. Recall, however that the proposed Bayesian adaptive design results in altered cell sizes such that the most promising treatment and placebo each receive an average of  $n = 60$  participants. (This is substantiated by the simulation results). Assuming  $n = 60$  participants per group and  $\alpha = 0.05$ , power to detect the difference between 0.25 and 0.50 is 81.80%, while power to detect the difference between 0.25 and 0.70 is > 99%. More generally, a sample of this size provide 80% power to detect the difference between 0.25 and 0.49 with  $\alpha = 0.05$ .

In summary, a Bayesian adaptive approach demonstrates adequate operating characteristics (Type I and II Error Rates) for the current trial. The method results in allocation of more participants to the most effective condition. Finally, the approach permits frequent analyses with more desirable Type I and Type II Error rates.

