### **General Data Analytic Strategies**

All statistical analyses will use SAS v. 9.2 (SAS Institute Inc., Cary, N.C.). Preliminary data analyses inspecting group differences on demographic and baseline variables will evaluate posterior distributions for differences in proportions and means, as well as for correlations between baseline variables and specified outcomes. Baseline or demographic variables for which the posterior distribution indicates there is > 99% chance of a difference across groups, and for which there is a > 99% chance of a non-zero correlation with outcomes, will be defined as potential confounders and will result in two sets of analyses: one in which the relevant variable is included as a covariate and one in which it is not. This will permit determination of the degree to which any group differences might confound conclusions regarding treatment.

Evaluation of the primary outcome, proportion of patients demonstrating > 50% decrease in depression scores on the MADRS, as a function of treatment will use a beta-binomial model and contingency tables with chi-square testing for Bayesian and Frequentist approaches respectively. Additional analyses will use the generalized linear modeling. Count, dichotomous and continuous Bayesian analyses will be conducted using Poisson (Proc GENMOD; SAS 9.2), logistic (Proc GENMOD; SAS 9.2), linear (Proc GENMOD; SAS 9.2) regression respectively. Distributional assumptions will be evaluated via inspection of residual plots and, where possible, by formal statistical tests. Violation of assumptions will be addressed, depending upon statistical technique, through the use of transformations, robust methods, and stratification.

Unless otherwise indicated in the data analytic plan, priors will be specified as neutral and diffuse. The beta-binomial model will use a  $\sim\text{Beta}(1,1)$  prior distribution. For linear, Poisson, and logistic regression, priors will take the form  $\sim\text{N}(0, 1 \times 10^6)$  in the linear, log, and log(odds) scales respectively. Convergence of Bayesian analyses on the posterior distributions via Monte-Carlo Markov chain (MCMC) will be assessed via graphical (Trace Plot, Autocorrelation Plot) and quantitative (Geweke Diagnostics, Gelman-Rubin Diagnostics, and Heidelberger-Welsh Diagnostics) evidence. Evaluation of posterior distributions will permit statements regarding the probability that effects of varying magnitudes exist, given the data.

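### The retained arm's effect is estimated partly from the interim data that selected it, with no selection-adjusted estimate planned; the bias is small if effects are large and material if they are small or null

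*Combined protocol and SAP*

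**What the plan says.** The Simulation Study section places the interim at 80 of 160 patients. If a decisive difference is found, "the algorithm then selected the treatment that had the highest posterior probability of conferring benefit". If none is found, aspirin is kept, to serve the programme's interest in that drug "by providing the most precise effect size estimate possible".

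After the interim, "The remaining 80 subjects were allocated to the retained (non-pruned) treatments". The chance of joining each arm then depends on how many arms are still open. The power paragraph then says that the design "results in altered cell sizes such that the most promising treatment and placebo each receive an average of" 60 patients.

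General Data Analytic Strategies specifies a beta-binomial model with Beta(1,1) priors and a chi-square test for the primary outcome. It adds: "Evaluation of posterior distributions will permit statements regarding the probability that effects of varying magnitudes exist, given the data". It also says that Bayesian interim analyses need no multiplicity adjustment, citing the likelihood principle.

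Estimation is a stated aim. The section on efficient drug development expects the same conclusions as a fixed design, "but with greater statistical precision for the most promising treatments". The reported operating characteristics cover how often a decisive difference and the combination were found. They do not cover bias or interval coverage.

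**The concern.** An arm that is kept because it looked best of three at 20 patients per arm has, on average, been lucky in those 20 patients, and the shared placebo group has been unlucky. If the same patients make up a third of the final comparison, a third of that luck passes into the final estimate. The aspirin fallback works the other way: aspirin is carried forward when every arm looked poor, so its pooled estimate tends to be low. Independent flat priors do not correct for either.

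The design is meant to show where Phase III resources should go. At stake is the size of the reported effect and the placement of its interval.

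**Working it through.** **Inputs, all from the Simulation Study section.** Total 160 in four arms; interim at 80; Beta(1,1) priors. Response rates for placebo, aspirin, NAC and combination: Scenario 1 0.25, 0.50, 0.50, 0.70; Scenario 2 0.25, 0.30, 0.30, 0.50; Scenario 3 (null) 0.25 throughout.

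**Cell sizes.** 80/4 = 20 per arm at the interim. With one active arm and placebo continuing, 80/2 = 40 each afterwards. 20 + 40 = 60, the plan's figure. Pooling is inferred from this sum; no sentence states it.

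**The plan's own power figure.** For 0.25 versus 0.50 at 60 per group, two-sided 0.05, mean rate 0.375:

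- null SE = sqrt(2 × 0.375 × 0.625/60) = 0.0884; alternative SE = sqrt((0.1875 + 0.25)/60) = 0.0854
- z = (0.25 - 1.96 × 0.0884)/0.0854 = 0.90, so power is 81.6%. The plan states 81.80%, so it is reproduced.

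**Two readings of the decisive rule.** The text gives two statements of the rule as equivalent, but they are not.

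- Reading A: decisive if any arm has posterior probability below 0.20 that its difference from placebo is under 10 points.
- Reading B: not decisive only if the posterior probability that all three differences are under 10 points exceeds 0.80.

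Results are given as A/B.

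**Method.** All 21^4 interim outcomes were enumerated exactly and the decisive, selection and fallback rules applied. At equal arm sizes the highest posterior probability of benefit is the highest responder count; ties were split equally. Later patients (40 per group) were added at the true rates. Monte Carlo simulation of the same design agrees to about 0.1 point.

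**Formulas**, with d the true difference:

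- bias of raw pooled difference = (20/60) × (mean interim difference on that route - d)
- posterior mean = (60/62) × raw difference, so its bias = (60/62) × raw bias - (2/62) × d

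Examples: under the null, reading A, the mean interim difference of a selected arm is 28.8 points, and 28.8/3 = 9.6. For the combination in Scenario 1, reading A, the raw bias is +1.1, so the posterior-mean bias is 0.968 × 1.1 - 0.032 × 45 = -0.4.

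**Results in percentage points (A/B).**

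| Route | Share of trials | Raw pooled bias | Posterior-mean bias |
|---|---|---|---|
| Scenario 1, decisive | 96%/>99.9% | +1.9/+1.5 | +0.4/+0.1 |
| of which combination chosen | | +1.1/+0.8 | -0.4/-0.7 |
| Scenario 2, decisive | 60.4%/98.9% | +4.1/+1.6 | +3.2/+0.9 |
| of which combination chosen | | +3.5/+1.0 | +2.6/+0.1 |
| Null, decisive | 12.4%/86.4% | +9.6/+3.8 | +9.3/+3.7 |
| Scenario 2, aspirin fallback | 39.6%/1.1% | -2.5/-8.9 | -2.6/-8.8 |
| Null, aspirin fallback | 87.6%/13.6% | -0.8/-6.0 | -0.7/-5.8 |

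If aspirin or NAC is selected in Scenario 2, the posterior-mean bias is +8.4/+4.7: a true 5-point benefit is reported as 13.4/9.7. Under reading B this happens in 2 × 8.0% = 16% of Scenario 2 trials.

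Under the null, the 95% credible interval of a selected arm covers the truth 81%/94% of the time.

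**Post-interim patients only (40 versus 40).** The raw difference has no selection bias, because these patients played no part in the choice. The interval is wider by about sqrt(60/40) = 1.22. In root mean squared error (RMSE) the pooled posterior mean is better in most branches: 7.8-8.2 against 10.0-10.4 points after a decisive interim in Scenarios 1 and 2, and 7.4 against 9.7 in the null fallback under reading A. The main exception is the decisive null branch under reading A, 11.3 against 9.7.

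**The case against.** The strongest reply is Bayesian. Given its prior, a posterior does not change because of the rule that chose the arm, and the plan cites the likelihood principle. This stands only in part. The plan uses the principle to decline a multiplicity adjustment, calls error probabilities essential when it reports its simulations, and also plans a frequentist analysis, for which the argument offers no cover.

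Three stronger readings are tempting, and the documents do not support them.

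- **A reader might infer that the reported benefit will always be too large after selection.** The planned posterior mean is slightly too small when the combination is chosen in Scenario 1, because Beta(1,1) shrinkage outweighs the selection effect there.
- **A reader might infer that the claims of precision are wrong and should be deleted.** Precision concerns spread, and the plan does not claim unbiasedness. The pooled posterior mean has the lower RMSE in most branches.
- **A reader might infer that the final test is undermined.** Over all routes under the null, the pooled chi-square test rejects 6.3%/6.2% of the time, against 5.2% for a fixed 60 versus 60 comparison. This point is about the estimate and its interval.

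It is also fair to say that the largest errors sit in uncommon branches (12.4% of null trials under A; 1.1% of Scenario 2 trials under B). Weighted over routes, the null posterior-mean bias is 0.124 × 9.3 - 0.876 × 0.7 = +0.5 (A) and 0.864 × 3.7 - 0.136 × 5.8 = +2.4 (B). But a reader of the final report sees one route, not the average.

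**Conclusion.** The point holds as a gap in the estimation plan. The retained arm's estimate reuses the data that selected it, and no selection-adjusted estimate is planned. If effects are as large as hoped, the planned posterior mean is off by about half a point or less on average in Scenario 1. The bias is material when effects are small or null (up to +9.3 points after selection), or when a single agent is chosen. After the fallback, aspirin's estimate is too low by amounts that depend strongly on the reading of the rule.

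These sizes assume 20 per arm at the interim, pooling as inferred from the 60 per group, one active arm retained, and the simplified trial of the Simulation Study section. They ignore the week-8 re-randomisation of non-responders, so they describe that model and not the full 16-week trial.

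The width of the ranges comes from the two statements of the decisive rule. Reading B matches the plan's Scenario 1 and 2 results (combination chosen 83.6% and 83.0%; plan 82.5% and 83%), but then 86.4% of null trials are decisive. Reading A gives 12.4%, and the plan reports a Type I error rate of 0.005. That conflict is a separate matter, but it decides how often each bias arises.

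**What to change.** Keep the pooled analysis and its power as planned. Add to General Data Analytic Strategies that:

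1. the retained arm's effect will also be reported with a selection-adjusted estimate and interval (a conditional or bias-corrected drop-the-losers estimator), covering both the selection and the aspirin-fallback routes;
2. the post-interim-only 40 versus 40 estimate will be shown as a sensitivity analysis;
3. the pooled estimate is not adjusted for selection. The existing wording on precision can stay with this note beside it.

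The cost is SAP text and some programming, with no added patients. The 40 versus 40 interval is about 22% wider and its RMSE is higher in most branches (about 10 against 8 points). Used alone it would also cut power for 0.25 versus 0.50 from 81.6% to 64.1%. It should therefore accompany the pooled estimate, not replace it.

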as adjunct to ongoing mood stabilizing medications in patients suffering from BD where there were significant effects on depressive symptoms. Recently, results of an open label study also revealed positive results on bipolar depression during a two month extension period [55]. Furthermore, these same authors demonstrated effects of NAC on certain symptomatic domains in patients with schizophrenia, primarily on negative symptoms [56].

**In view of these compelling preclinical and clinical observations, a study to test whether aspirin and NAC will ameliorate BD symptoms is highly warranted.** Our study will include measurements of cytokines, inflammatory factors and markers of oxidative stress **at baseline, at 8 wks and at 16 wks** to test the hypothesis that these are mediators or modulators of therapeutic response. Our proposed study will investigate the role of neuroinflammation and oxidative stress in antidepressant response in BD and could lead to the development of new therapeutic agents for patients that may enhance or replace failed responses to commonly used medications.

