### **Specific Aims**

We propose to conduct a double-blind placebo-controlled trial with a widely available and prototypical non-steroidal anti-inflammatory agent, aspirin, and an antioxidant agent, NAC, involving symptomatic BD type I and II patients having a depressive or mixed episode. This will be the first controlled study to test the hypothesis that aspirin and NAC, by themselves or in combination, will be beneficial in treating depression in bipolar disorder patients and in promoting mood stabilization. We propose to utilize a novel drop-the-loser (DTL) adaptive design that will be more cost-effective in screening new medication leads.

Our study has the following Aims: Aim I – Examine efficacy of aspirin in treating depression in bipolar patients in a double-blind placebo-controlled add-on design; Aim II – Examine efficacy of NAC in treating depression in bipolar patients in a double-blind placebo-controlled add-on design; Aim III – Examine efficacy of combined treatment with aspirin and NAC looking for synergistic, potentiating effects; Aim IV – Examine the role of markers of neuroinflammation, oxidative stress and cytokines as possible mediators or modulators in therapeutic response in the treatment of depression in patients with BD.

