During the first 8-week trial, patients will be seen at weeks 0, 1, 2, 3, 4, 6 and 8 for clinical assessment and mood ratings. During the continuation trial, they will be seen at weeks 8, 10, 12, 14 and 16. The main outcome measure for the study will be the scores on the Montgomery-Asberg Depression Rating Scale, MADRAS [62]. All patients will also be assessed with the Young Mania Rating Scale, YMRS [63], the Clinical Global Impression-Bipolar version, CGI-BP [64], and the UKU side-effects scale [65]. In all visits, patients will be seen by the study psychiatrist and the research staff will complete mood ratings with the MADRAS, YMRS, CGI-BD, and the UKU side-effects scale.

At baseline (before randomization), week 8 and week 16 blood will be sampled for proinflammatory markers (C-reactive protein, soluble interleukin (IL)-2 receptor, IL-6 and tumor necrosis factor (TNF)-alpha), and oxidative stress

markers (superoxide dismutase activity and catalase activity, serum thiobarbituric acid reactive substances (TBARS)), which have been reported to be elevated in BD patients [34] [33] [35]. These blood samples will be stored for possible future research on biomarkers or future genetic studies for up to 20 years, for use in pharmacogenetic research during this 20 year timeframe. The samples will be stored at the Wet Lab, in a double locked -80 degrees freezer, at [REDACTED]

[REDACTED] for future use studying factors of Bipolar Disorder. When (or before) the 20 year period ends, the blood sample will be destroyed.

Patients will complete neuropsychological testing at baseline and Week 16. The testing will include CANTAB, WASI, and WRAT assessments and will take approximately 3-4 hours.

At the screening visit, week 8, and week 16 we will also be testing the Lithium levels in all patients that have been prescribed and currently taking the medication for study purposes. This extra test will be conducted for the safety of the patient and more Lithium level tests can be ordered under the PI's discretion throughout the 16 week trial.

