Interim Bayesian analysis with application of pruning/retention rules will be conducted when 50% of randomized subjects have reached (or should have reached) the end of study. If, at 50% of data gathering, there are additional participants continuing in active treatments that might be pruned, sensitivity analyses will inspect the degree to which potential results from these active patients might alter the conclusions of the interim analysis. If necessary, randomization will be temporarily suspended and data gathering will continue until sensitivity analyses demonstrate that statistical conclusions will remain unchanged by any patients who have not yet completed treatment. While Frequentist approaches require adjustment for multiple testing when conducting interim analyses, no such adjustment is necessary for Bayesian analyses due to its conformity to the likelihood principle [57]. Further, Monte Carlo simulations (conducted in SAS v. 9.2) demonstrate that Type I and Type II Error Rates are at appropriate levels for the proposed design (see Simulation Study). Intention to treat principles will apply at both the interim and final analysis points; any patients having dropped out of the study will be counted as non-responders.

Structural Equation Modeling/Path Analysis will evaluate the degree to which inflammatory cytokines and markers of oxidative stress mediate the effect of treatment on MADRAS. Estimation of SEM/Path Models will employ both Frequentist and Bayesian approaches. In the context of the direct effects of treatment, mediational modeling will permit estimates of the indirect effects of treatment on MADRAS scores via inflammatory cytokines or markers of oxidative stress using the product coefficient method [68]. Frequentist ninety-five percent confidence intervals for maximum likelihood estimates will be constructed using a bootstrap resampling approach [69]. Bayesian SEM estimates for indirect effects will employ the posterior distribution of the product coefficient. All SEM/Path analyses will be conducted in MPlus v. 6.0 [70].

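### The Aim IV mediation model fixes no marker visit, MADRS visit, treatment assignment or mediation-specific baseline adjustment, so its indirect effect is open to confounding and, at week 16, to heavy dilution

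*Combined protocol and SAP*

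**What the plan says.** Aim IV in Specific Aims is to "Examine the role of markers of neuroinflammation, oxidative stress and cytokines as possible mediators or modulators in therapeutic response". Introduction and Background says the samples are taken "to test the hypothesis that these are mediators or modulators of therapeutic response". Study procedures sets the times: "At baseline (before randomization), week 8 and week 16 blood will be sampled for proinflammatory markers". MADRS is rated more often. In the first period "patients will be seen at weeks 0, 1, 2, 3, 4, 6 and 8 for clinical assessment and mood ratings"; in the second "they will be seen at weeks 8, 10, 12, 14 and 16".

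Under Study Design, responders at week 8 keep their drug and "the non-responders will be re-randomized for one of the other three groups".

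The only marker-specific analysis is in General Data Analytic Strategies. A structural equation or path model will "evaluate the degree to which inflammatory cytokines and markers of oxidative stress mediate the effect of treatment on MADRAS", using the product of coefficients, bootstrap intervals and a Bayesian counterpart. It names no marker sample, MADRS visit, assignment (first or second) or covariate.

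The same section has one general covariate rule. A baseline variable is adjusted for only if the posterior probability of a group difference and that of a non-zero correlation with outcome both exceed 99%; the analysis is then run with and without it. No treatment-by-marker interaction or other moderator analysis is described, only a general mention of generalized linear models.

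**The concern.** A product-of-coefficients estimate multiplies two paths: treatment to marker, and marker to outcome given treatment. Randomisation protects the first path only. Patients who start with higher marker levels or higher MADRS may have higher later values of both. Unless the model conditions on those baselines, that alone can produce an apparent indirect effect.

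The open choice of visit adds a second problem. By week 16 many patients have changed arm because of their week-8 outcome, so the meaning of *treatment* depends on which assignment is used. Leaving visit and assignment open also lets them be chosen after the results are seen.

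At stake is the mechanistic conclusion that Aim IV promises, and its *modulator* part has no analysis at all.

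**Working it through.** The plan gives no power, sample size or effect size for the mediation analysis, so it has no figure of its own to reproduce here.

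**1. Inputs.** From Statistical analyses: 160 patients, 40 per arm. Response rates for placebo, aspirin, NAC and combination are 0.25/0.50/0.50/0.70 (Scenario 1), 0.25/0.30/0.30/0.50 (Scenario 2) and 0.25 throughout (Scenario 3). After pruning, placebo and the best arm average 60 each, leaving (160 − 120)/2 = 20 in each other arm if these are equal. Assumptions: the rates apply at week 8, all responders stay (placebo included), all non-responders are re-randomised with every other arm open, and nobody drops out.

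**2. Share on a different arm at week 16** = Σ n_arm × (1 − response rate) / 160.
- Scenario 1: 40 × (0.75 + 0.50 + 0.50 + 0.30) = 82, or 51%.
- Scenario 2: 40 × (0.75 + 0.70 + 0.70 + 0.50) = 106, or 66%.
- Scenario 3: 40 × (4 × 0.75) = 120, or 75%.
- With cells of 60/20/20/60 (combination as best arm): 83 (52%), 103 (64%) and 120 (75%).

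**3. What remains of the first-assignment contrast.** Assume equal re-allocation over the other three arms. Of the original placebo arm, 0.75 × 2/3 = 50% are on an aspirin-containing arm in weeks 9 to 16. Of the original combination arm, the share is:
- Scenario 1: 0.70 + 0.30/3 = 80%.
- Scenario 2: 0.50 + 0.50/3 = 67%.
- Scenario 3: 0.25 + 0.75/3 = 50%.

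The difference in aspirin exposure falls from 100 points to 30, 17 or 0.

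**4. How often the covariate rule would act.** With diffuse priors and true randomisation, a posterior probability above 99% in one direction arises by chance in about 1% of two-arm comparisons, or about 2% counting both directions. If any of the six pairwise comparisons counted, the chance for a given variable would be at most 6 × 2% = 12%. The correlation condition lowers it further, and even then the unadjusted analysis is also run.

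**5. What omitting baseline can do (illustration; all coefficients assumed, none from the documents).** Let the baseline marker have SD 1 and contribute 0.3 to baseline MADRS. Let each week-8 value carry over 0.5 of its own baseline, with residual SD 0.8. Let treatment move the marker by −0.6, and let the marker have no effect on MADRS, so the true indirect effect is 0.
- Unadjusted marker-to-MADRS slope: (0.5 × 0.3 × 0.5)/(0.25 + 0.64) = 0.075/0.89 = 0.084. Product: −0.6 × 0.084 = −0.05. With baseline marker and MADRS in both equations it is 0.00.
- Add an unmeasured common cause loading 0.4 on every marker and MADRS value. Its total weight is 0.4 + 0.5 × 0.4 = 0.6 on the week-8 marker and 0.4 + 0.5 × (0.4 + 0.3 × 0.4) = 0.66 on week-8 MADRS. The slope becomes (0.075 + 0.6 × 0.66)/(0.25 + 0.36 + 0.64) = 0.471/1.25 = 0.377, and the product −0.6 × 0.377 = −0.23.
- Simulating that second case with 200,000 patients gave −0.23 unadjusted and −0.10 baseline-adjusted at week 8. At week 16 it gave −0.17 by first arm and −0.27 pooled by current arm. The week-16 treatment-to-marker path was about −0.40, against −0.6 + 0.5 × (−0.6) = −0.90 had everyone stayed on their arm.

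**6. Time order.** Week 8 is the only post-baseline sample in the first period and coincides with the week-8 MADRS; the ratings at weeks 1 to 6 precede it. The ratings at weeks 10 to 16 follow it, but across the re-randomisation.

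**The case against.** A reader might infer that any week-16 mediation estimate is biased whichever assignment is used. The documents do not support that. By first assignment, the treatment-to-marker path at week 16 is still randomised; it is diluted and refers to a sequence that begins with that arm. Among non-responders, the second assignment is random given the first arm. Only pooling stayers and switchers by current arm loses randomisation, and the plan does not say it will do this. For the same reason, making week-16 markers purely descriptive would discard a randomised comparison in roughly 82 to 120 patients.

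A reader might also infer that the plan has no baseline adjustment at all. It has the conditional rule, but that rule serves a different purpose.

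The switching shares measure exposure change, not bias, and matter only if week-16 data enter the model. In the illustration, week 16 by first arm (−0.17) lies nearer zero than unadjusted week 8 (−0.23). This is because the treatment path shrank; the marker-to-MADRS slope was no less confounded (0.417 against 0.376).

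Two further points stand. A week-8 model does not create time order, and reversing the marker–MADRS arrow would fit the basic path model equally well. Seven named markers by three active arms would give 21 interaction terms at about 40 patients per arm, which is too many to add without limits. Aim IV is also mechanistic and hedged in its wording.

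**Conclusion.** The concern holds as a specification gap with a confounding consequence. Visit, assignment and baseline covariates are all open, and the one covariate rule would seldom supply the adjustment that the marker-to-MADRS path needs. The documents do not allow the resulting bias to be sized; the illustration shows only that a spurious indirect effect can arise and that baseline adjustment reduces it without always removing it.

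The week-16 figures (51%, 66% and 75% switched; aspirin contrast down to 30, 17 or 0 points) rest on the assumptions in the working. The plan states no dropout rate. If dropouts are counted within the non-response rates, fewer patients are actually re-randomised.

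Study Design keeps every responder on the same drug, while Study procedures refers to responders on active medication. These passages must be reconciled, because they determine who changes arm.

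The gap limits the mechanistic conclusions and leaves the primary response comparison untouched. It is worth correcting before unblinding.

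**What to change.** In General Data Analytic Strategies:

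- **Main mediation model:** first randomised assignment, week-8 marker and week-8 MADRS, with baseline marker and baseline MADRS always in both the marker and the outcome equations, whatever the general covariate rule gives. State how missing markers are handled.
- **Interpretation:** state that marker and outcome are concurrent, and that the result is association consistent with mediation under no unmeasured marker–outcome confounding. Add a sensitivity analysis for that assumption.
- **Week 16:** use these markers inferentially only in a secondary stage-wise analysis of re-randomised non-responders, by second assignment, conditioning on first arm and with week-8 values as baseline. Do not fit a pooled as-treated model. Precision will be low: 82 to 120 patients over 4 × 3 = 12 arm sequences average about 7 to 10 each.
- **Modulators:** either name a limited, exploratory set of treatment-by-baseline-marker terms, or remove the word from Aim IV.

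The cost is plan wording and slightly more analysis work. No new samples or visits are needed. The downside is fewer inferential uses of the week-16 markers.
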